The robot can tell stories, play music (according to older adults' preference) and remind older adults about date and time of the social events/health activities. Quizzes can be tailor-made by family members according to older adults' understanding and cognitive ability.

3. Socially connect to family members or friends: making phone calls

[figure not shown]
This feature provides connectivity services to reduce older people's social isolation and help foster connections with family, friends and community. The phone application

inside the robot connects the older adults with family members, relatives and friends, extending their social connections.

[figure not shown]
4. Promoting Healthy Lifestyle

The robot has an exercise system which encourages older people to exercise regularly. It will remind the older adults about daily health-related activities: drinking water, doing exercise and reading books.

Interactive modalities

The robot can talk, sing, play games, report weather and read the news. Older people can communicate with the robot via voice commands or a touch panel.

Aims of the study

This study aims to investigate the feasibility and acceptability of home-based physical robot HUMANE by community-dwelling Chinese older adults and soon-to-be-aged adults.

Objectives of the study

The objectives of the study are:

1. To investigate the feasibility of using different features of this robot HUMANE at home within 6 weeks;
2. To investigate the acceptability of the robot at home by older adults, their spouse, and other family members;
3. To assess the preliminary efficacy of this robot on loneliness, depression and mood and calculate the effect size of the use of the robot at home for a full RCT.

Methods

Study design

This study will employ a two-arm pilot randomized control trial with qualitative interviews.

Participants

The participants of this study are people aged 50 or above who are receiving home care from family members. Purposive sampling will be adopted in recruitment. We purposively look for people with different gender, age groups (20 people per each age

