group: 50-60 years; 60-70 years; and 70-80 years), educational backgrounds and occupations, to reflect a diversity of views from the aged population. We will also recruit six computer ambassadors from a non-government organization in Hong Kong; these ambassadors have at least one-year experience in computer use. The ambassadors will be trained to support the study participants to use the robot during the intervention period.

As a pilot RCT study, a minimum sample size between 24 and 50 have been recommended.^{16 17} In this study, a total of **60 community-dwelling soon-to-be-aged or older adults** will be recruited. They would be randomized to two groups (intervention group, IG, and control group, CG), that is, 30 adults will be randomized to IG while the other 30 adults will be assigned to CG. Thirty family caregivers will also be recruited through participants assigned in IG group.

The inclusion criteria

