1.2 For family caregivers

- Live with the participating older adult in the same household or in other household but with regular contacts (at least once per week) with the participating older adults
- Are able to communicate in Cantonese or Putonghua

The exclusion criterion for the participants are those:

- With acute mental disorders or disabling diseases that may limit the practice of engaging with robot; and
- have limited access to electricity and this makes them hard to use technology at home.

Intervention

The robot HUMANE will be used by the IG (30 participants) for an 6-week trial. Project team will set up a physical robot at their homes. Each participant will be given a protocol to engage with different features of the robot every day. Participants are asked to complete the assigned daily tasks at their own homes. **Table 1** shows the 6-week tasks with the robot HUMANE.

Phone counselling will be given to support the study participants by the trained ambassadors. A training workshop will be given to the ambassadors by the technical team before the intervention starts. A hotline will be set up for the participants and volunteers during the trial period to provide technical support. Participants will be encouraged to contact the ambassadors if they need support and when they had completed daily tasks. The ambassadors will contact the assigned participants (one ambassadors will be assigned with 5 participants) every three days by phone to ensure continued participation and to follow up on their progress.

Table 1. 6-week tasks of engaging with the robot HUMANE

Days	Tasks
Week 1	
• Set up the robot• Complete the baseline assessment[#]
Week 2	
• Explore the features of the robot with the caregiver• Talk to the robot
Week 3	
• Communicate with two relatives using the robot• Record the appointments in the next 2 months
Week 4	
• Check the calendar, weather forecast and read news• Search and listen music with the robot• Do 30-minute exercises with the robot
Week 5	
• Check the calendar, weather forecast and read news• Play games with the caregiver on the robot• Communicate with a friend using the robot• Perform a task according to the calendar• Play cognitive training games with the robot

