The perspectives and experience of using home-based robot HUMANE will be collected from home care receivers and their family caregivers through a 30mins in-depth individual interview. The questions that will be asked are framed with reference to the guideline on feasibility studies for intervention trials¹⁹. The guiding questions are as follows: 1) Acceptability: what do you think about the acceptability or satisfaction of using the robot at home? 2) Integration: what do you think if the robot can be integrated into the normal routine of your life? 3) Practicality: what are the practical concern regarding the robot? 4) Efficacy: what changes do you have after you have engaged with the robot (for family caregiver: what changes do you observe the family member have after engaged with the robot)? The interview will be ceased until research team were satisfied that thematic saturation²⁰ was reached.

Recruitment Rate

Research assistant will maintain a detailed record of the total number of target population accessed, recruited and retained. The study costs, human resources, the time taken for recruitment, the number of contacts, visits, the challenges encountered, reasons for withdrawal from the study, and factors that influenced recruitment and study completion rates will be recorded accordingly.

Outcome measures in pilot RCT

The following outcomes will be measured: 1) loneliness, 2) cognitive function, 3) emotional status, 4) self-efficacy, 5) social capital and 6) mutuality. The measurements will be utilized at baseline (day-1) and immediately post-intervention (week-6) to examine preliminary effect of using robot at home.

Loneliness

The loneliness status of participants will be explored to inform the selection of outcome measures in a full RCT to assess the effectiveness of the intervention. The 6-item Chinese de Jong Gierveld Loneliness Scale ²¹ consists of emotional loneliness and social loneliness two subscales, each of them contains three items. They are three response categories for each item: “no”, “more or less”, and “yes.” The scale has been validated and recommended as a reliable (Cronbach’s α of the 6-item scale was 0.76, the intra-class correlation coefficients ranged from 0.98 to 1.00) and valid (the content validity was high as shown by the results of the Delphi panel) measure of loneliness in older Chinese ²¹.

Cognitive function

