In this study, a 5-item Abbreviated Memory Inventory for the Chinese (AMIC) 16 will be used to assess participants’ cognitive function. AMIC is an abbreviated version of the original 27-item Memory Inventory for Chinese people, with a sensitivity of 54.6%-65.3% and specificity of 57.4%. There are five items: “Do you always forget where you put your stuff?”, “Do you feel that your memory is worse than your peers?”, “Do you always forget what you want to say during a conversation?”, “Do you always fail to find the appropriate word to express your idea during a conversation?”, and “Do you forget your acquaintances’ names when you meet them?”. AMIC scores range from 0-5 (1 point for each item; 0-best to 5-worse). An AMIC score ≥ 3 is predictive of MCI.

Emotion status

The Chinese version of 2Q questionnaire was chosen because of the high sensitivity and that it was simple to use²². The 2Q was derived from the Primary Care Evaluation of Mental Disorders Procedure (PRIME-MD). The questionnaire includes two questions about depressed mood and anhedonia: "During the past month, have you often been bothered by feeling down, depressed, or hopeless?" and "During the past month, have you often been bothered by little interest or pleasure in doing things?" It is recommended a useful measure for screening depression in primary care in Hong Kong²².

Self-efficacy

The Chinese version of the General Self-Efficacy Scale is a reliable and valid scale that can be used with confidence in community Chinese soon-to-be-aged adults²³. The CGSE Scale consists of 10 items that measure a generalized sense of competence. All items are rated on a 4-point Likert scale ranging from 1='Not at all true' to 4='Exactly true'. The higher the score, the greater self-efficacy the respondents possess.

Social capital

Social capital will be evaluated using the social capital scale to cover the two dimensions of social capital (social cohesion and social interaction) developed by Mujahid ²⁴. The social cohesion subscale consists of 4 items: 1) People around here are willing to help their neighbors, 2) People in my neighborhood generally get along with each other, 3) People in my neighborhood can be trusted, 4) People in my neighborhood share the same values. Each item ranged from 1 to 5 (1 = strongly disagree, 2 = disagree, 3 = neutral, 4 = agree, and 5 = strongly agree). Cronbach's alpha was 0.81 among the Chinese community-dwelling older adults²⁵.

Mutuality

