Mutuality was assessed with the Chinese version of the Mutuality Scale, which consisted of questions related to love, shared activities, values, and reciprocity ²⁶. Each item was rated with a 5-point Likert scale ranging from 0 ("not at all") to 4 ("a great deal"); the total score was the mean of all items (ranging from 0 to 4). Higher scores implied greater

mutuality. Cronbach's alpha was 0.96 for dementia patients and 0.94 for caregivers respectively²⁶.

Data analysis

SPSS Statistics 26 will be adopted for all analyses. Descriptive statistics will be used to summarize the participant characteristics. Differences between the intervention and control groups in relation to outcome measures will be compared across multiple time points using generalized estimating equations (GEE) models or generalized linear mixed model (GLMM). The effect size will be computed to show the magnitude and direction of the effect of the intervention group relative to the control condition for each outcome variable. The usage statistics will be calculated and used to reflect the feasibility of the intervention. A deductive content analysis approach will be used to analyze the transcribed interview verbatim in relation to the feasibility of the intervention, which is considered suitable for a detailed analysis of the four indicators of the feasibility of the intervention: acceptability, integration, practicality, and efficacy¹⁹.

Ethical and safety considerations

Ethics approval and permission will be obtained from the study university before study undertaken. The research participants' privacy, safety, health, social sensitivities, and welfare will be adequately protected according to the university ethics' requirements. There will be no serious risks anticipated for this research. The surveys and interviews were not designed to place participants in an uncomfortable position. Researchers will provide participants with contact details for the study if they have any concerns.

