Before enrolment into this study, all participants will give written informed consent and they will be free to refuse to any assessments and withdraw from the study at any time. All study documents will be stored in a locked filing cabinet at the study university. Only the project team members have access to the consent forms. All study relevant data will be permanently deleted by the primary researcher after 7 years. Confidentiality will be maintained through replacing all names of individuals with pseudonyms and changing any potentially identifiable details in the transcripts and any reports, presentations, or publications arising from the research.

Study timeline

month	1	2	3	4	5	6	7	8	9	10	11	12
Recruit research staff	x											
IRB submission and approval	x											
Recruit 60 participants	x											
Training for 6 ambassadors	x	x										
6-week trial for using the robot (1-10 participants)			x	x	x							
6-week trial for using the robot (11-20 participants)					x	x	x					
6-week trial for using the robot (21-30 participants)							x	x	x			
Baseline assessment			x		x		x					
Post-intervention assessment					x		x		x			
Qualitative interviews			x	x	x	x	x	x				
Data analysis				x	x	x	x	x	x	x	x	
Report preparation and results dissemination										x	x	x

Reference

1. Census and Statistics Department. Population by Sex and Age Group 2021 [Available from: https://www.censtatd.gov.hk/en/web_table.html?id=1A accessed 30 October 2021.
2. Census and Statistic Department. Population Projections Census and Statistic Department Web site2017 [Available from: <https://www.censtatd.gov.hk/en/EIndexbySubject.html?PCODE=FA100061&SCODE=190> accessed 30 October 2021.
3. Census and Statistic Department. Domestic Households in Hong Kong. Retrieved from HKSAR Census and Statistic Department Web site2016 [Available from: <https://www.bycensus2016.gov.hk/en/Snapshot-04.html> accessed 30 October 2021.
4. Elderly Commission. Report on Healthy Ageing Executive Summary 2021 [Available from: <https://www.elderlycommission.gov.hk/en/library/Ex-sum.htm> accessed 23 Nov 2021.
5. Gasteiger N, et al. Older adults' experiences and perceptions of living with Bomy, an assistive dailycare robot: a qualitative study. *Assistive Technology* 2021 doi: 10.1080/10400435.2021.1877210

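### Free precision gain: with only baseline and week 6 measured, define each scale effect as the week-6 group difference adjusted for baseline

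*Protocol*

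**What the plan says.** The protocol's section on outcome measures in the pilot RCT fixes two assessments: "The measurements will be utilized at baseline (day-1) and immediately post-intervention (week-6". The study timeline agrees. It has one row for the baseline assessment and one labelled "Post-intervention assessment", so there is a single post-baseline time point.

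Data analysis then says that differences between groups will be "compared across multiple time points using generalized estimating equations (GEE) models or generalized linear mixed model (GLMM". It adds that an effect size will show the "magnitude and direction of the effect of the intervention group relative to the control condition for each outcome variable". It does not say which model term is the effect, or whether the baseline score enters as a covariate.

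Objective 3 gives the estimate its use: to "calculate the effect size of the use of the robot at home for a full RCT". On numbers, the Participants section says "30 adults will be randomized to IG while the other 30 adults will be assigned to CG".

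**The concern.** In a repeated-measures GEE or mixed model, the term most often reported as the treatment effect is group by time. With two visits, that term is the difference between arms in mean change. It is unbiased under randomisation. But it subtracts the whole baseline score, when only the part that predicts week 6 helps. Unless the two scores are very highly correlated, the subtraction adds noise that regression on baseline would avoid.

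The stake is the precision of the effect sizes that the pilot is meant to pass on. With 30 per arm these are imprecise under any analysis, and the baseline scores that would sharpen them are already collected.

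**Working it through.** **Inputs from the protocol.** Two assessments (Outcome measures in pilot RCT; Study timeline) and n = 30 per arm (Participants). The total of 60 = 30 + 30 rests on a cited pilot recommendation of 24 to 50, not on a power calculation, so there is no power figure to reproduce.

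**Assumptions.** The baseline to week-6 correlation ρ is not given; 0.3, 0.5, 0.7 and 0.8 are used. SD is 1 at both visits, the link is identity and data are complete.

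**Step 1: what the group-by-time term estimates.** Two groups at two visits give four means. The interaction is (IG week 6 − IG baseline) − (CG week 6 − CG baseline), the difference in mean change. In 400 simulated complete-data trials the GEE coefficient matched this to within 2.3e-16.

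**Step 2: variances.**
- Difference in mean change: (2/n) × 2(1 − ρ)
- Week-6 difference adjusted for baseline: (2/n) × (1 − ρ²)
- Ratio: 2(1 − ρ)/(1 − ρ²) = 2/(1 + ρ), which is 1.54, 1.33, 1.18 and 1.11

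**Step 3: small-sample cost.** Estimating the baseline slope inflates the adjusted variance by 1 + 1/(2n − 4) = 1 + 1/56 = 1.0179. The ratio becomes 2/[(1 + ρ) × 1.0179].

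**Step 4: confidence intervals.** Mean half-width = t × SE × (1 − 1/(4 df)). The last factor is the average shortfall of an estimated SD. There are 58 df for change and 57 for the adjusted analysis; t is 2.002 for both. At ρ = 0.5:
- Change: SE = √(2/30 × 1) = 0.2582, and 0.2582 × 2.002 × 0.9957 = 0.515
- Adjusted: SE = √(2/30 × 0.75 × 1.0179) = 0.2256, and 0.2256 × 2.002 × 0.9956 = 0.450

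| Assumed ρ | Variance ratio, change to adjusted | Half-width, change (SD) | Half-width, adjusted (SD) | Narrower by |
|---|---|---|---|---|
| 0.3 | 1.51 | 0.609 | 0.495 | 19% |
| 0.5 | 1.31 | 0.515 | 0.450 | 13% |
| 0.7 | 1.16 | 0.399 | 0.371 | 7% |
| 0.8 | 1.09 | 0.325 | 0.312 | 4% |

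**Step 5: break-even.** The ratio equals 1 at ρ = 2/1.0179 − 1 = 0.965. Above that, adjustment costs a little: the ratio is 2/(1.98 × 1.0179) = 0.992 at ρ = 0.98 and 2/(2 × 1.0179) = 0.982 at ρ = 1. The loss is under 2% of variance.

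**Step 6: simulation.** With 40,000 bivariate normal trials per ρ at 30 per arm, the ratios were 1.505, 1.304, 1.161 and 1.094. Coverage was 94.9% to 95.2% for both analyses. For short bounded scales (the protocol says "AMIC scores range from 0-5 (1 point for each item; 0-best to 5-worse"), a score built from five yes/no items with mean 1.1 gave 1.53, 1.31 and 1.21 at ρ of 0.31, 0.53 and 0.64. With mean 2.5 it gave 1.49, 1.26 and 1.17 at 0.34, 0.56 and 0.68. Coverage was 94.7% to 95.2%.

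**Step 7: unequal SDs.** With SDs s₀ at baseline and s₁ at week 6, the variance of change minus the adjusted variance is proportional to s₀² + s₁² − 2ρs₀s₁ − s₁²(1 − ρ²) = (s₀ − ρs₁)². This is never negative, so, apart from the slope cost in Step 3, the direction does not depend on equal SDs.

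**The case against.** The strongest objection is that this is ordinary SAP content. The protocol names a model family, does not forbid baseline adjustment, and may have an SAP that names the contrast. That stands as far as error goes: nothing is stated wrongly. What remains is a better definition, at no cost, of a deliverable that the protocol itself sets in objective 3.

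The second objection is that the comparator is assumed. Data analysis never commits to group by time. If the team already intends to regress week 6 on group and baseline, or to constrain the baseline means to be equal, there is little or nothing to gain. This stands, and the gain is therefore conditional. A reader might turn the ratios into participants wasted by the plan; the text does not support that, because it does not choose the less precise contrast.

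Third, ρ is unknown. The Loneliness section quotes intra-class correlation coefficients of 0.98 to 1.00. Their type is not stated, and the same sentence gives a Cronbach's alpha of 0.76, so they do not fix the six-week correlation. If they did reflect six-week stability, adjustment would gain nothing for that scale.

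Fourth, the protocol's main aim is feasibility and acceptability, efficacy is called preliminary, and naming the contrast does not settle how an effect is standardised. All true; these points limit the weight of the suggestion, not its correctness.

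A reader might also infer that a comparison over multiple time points means a group effect averaged over both visits, which would halve a true week-6 effect (0.25 for 0.50 SD in simulation). The wording does not say so. Nor does it conflict with a two-visit schedule, since two visits are multiple.

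**Conclusion.** This is a worthwhile free improvement, not a correction. If the planned comparison is the group-by-time term, adjusting week 6 for baseline narrows the 95% confidence interval by 19% at ρ = 0.3, 13% at 0.5, 7% at 0.7 and 4% at 0.8. There is no gain above about 0.965, and any loss there is trivial. The gain is useful at low or moderate correlation, small at 0.7 to 0.8, and could be negligible for loneliness.

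The result rests on an assumed ρ, complete data and an identity link, and it covers scale scores only. The algebra does not carry over to a yes/no outcome from the 2Q. A reader might conclude that the planned analysis is biased or invalid. It is not: both contrasts are unbiased for the same week-6 effect under randomisation. The sample size of 60 is unaffected.

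**What to change.** Add to Data analysis: for each scale outcome, the intervention effect is the week-6 difference between groups adjusted for that scale's baseline score, reported with a 95% confidence interval and used for objective 3. ANCOVA does this. So does a GEE or GLMM with week 6 regressed on group and baseline, and a two-visit model with baseline means constrained equal targets the same effect. The named model families can therefore stay.

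State also that the baseline is the day-1 assessment, taken before exposure to the robot. Table 1 lists robot set-up and "Complete the baseline assessment" together as Week 1 tasks, and a baseline taken after exposure could absorb part of the effect.

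The 2Q outcome and the handling of missing week-6 scores can stay with the SAP. The cost is one or two sentences and one degree of freedom per model, with no added visits, data or participants.
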